3.7 Changes in the Conduct of Study or Planned Analysis compared to protocol/CIP

This SAP implements the subsequent deviations and clarifications from the analysis specification of the study protocol:

- For the SAP, study endpoints are presented as provided in the protocol synopsis and protocol section 2 (study objectives).
- Definition of Screen Failures. In the study protocol (section 10.1.1) a screen failure is defined as patient who is not eligible, i.e. is not respecting all the inclusion/exclusion criteria. According to the study protocol, such patients should not be randomized and enrolled.
To streamline presentation of patient flow for reporting and to extend definition also for protocol deviations, screen failure will be defined as screened patients, who are not randomized. By this, patients, who were randomized although they did not comply with eligibility criteria will not be considered as screen failure. On the contrary, patients, who comply with all eligibility criteria but dropped out from the study before randomization (e.g. due to consent withdrawal) will be considered as screen failure.
- Definition of compliance: in section 10.3, the study protocol demands further compliance definitions based on diary card information to investigate compliance with study eye treatment. However, as no eye-specific assessments were recorded on diary card, no such definitions were established.
- In the study protocol, no inferential analyses are specified. However, purely exploratory 95% confidence intervals and hypothesis testing for the difference between treatment groups will be implemented in the SAP on sponsor's request. These inferential procedures will be purely exploratory without adjusting for type I error rate.

4 General Definitions

4.1 Report Language

All TLFs will be prepared in English.

4.2 Analysis Software

The statistical analysis will be performed using the SAS[®] statistical software package (Statistical Analysis System, Version 9.3 or later).

5 Data Preparation

5.1 Data Handling and Medical Coding

For data quality control and medical coding please refer to the Data Management Plan including the Data Validation Plan in its most recent version.

5.2 CDISC

All output as defined in the SAP will be generated based on CDISC ADaM datasets following ADaM implementation Guide 1.0, as per contract with Dompé farmaceutici S.p.A.. SDTM programming will follow SDTM version 1.3 together with SDTM implementation guide 3.1.3.

Specifications for the ADaM datasets (as well as SDTM datasets) are described in a separate document.

5.3 SAS-Programming Quality Level

The following quality level of programming deliverables will be applied, as per contract with Dompé Farmaceutici S.p.A.. All statistical output will receive a tailored Quality Control (QC) approach by:

- Full independently double programmed reproduction (QC) of CDISC:
 - SDTM datasets
 - ADaM datasets
- Full independently double programmed reproduction (QC) of results of all tables and inferential analyses
- Listings will not be double programmed. However, complex listings for BDRM requiring a complex selection will undergo a fully independent double programmed QC.
- All tables and listings will undergo comparison with specification (i.e. SAP and templates), cross checking with other tables and listings, a sensibility review and SAS-log review by a senior statistician.

6 Analysis Sets and Subgroups

6.1 Analysis Sets

A patient will be defined as *screened* after the signature of the informed consent, regardless of the completion of all the screening procedures. A patient will be defined as screen failure, if he was screened but not enrolled in the study.

Enrolled Set:

A patient will be defined as *enrolled* in the study if he/she is randomized. This analysis set will be used for presentation of study disposition.

If not stated otherwise, analyses based on the Enrolled Set will be summarized by the treatment randomized.

Safety Set (SAF):

The Safety Set will be defined as all enrolled patients who receive at least one dose of the investigational medicinal product (IMP) at the study eye(s). *This analysis set will be used for the demographic, baseline and background characteristics and safety analysis.* All analyses based on the SAF will be summarized by the treatment received.

Full Analysis Set (FAS):

The Full Analysis Set will be defined as all patients in the SAF, who have at least one post-baseline efficacy measurement in a study eye. This analysis set will be used for the primary and co-primary efficacy analysis and all other efficacy analyses. All efficacy analyses based on the FAS will be summarized by the treatment randomized.

Per Protocol Set (PPS):

The Per Protocol Set will be defined as *all patients in the FAS who fulfill the study protocol requirements in terms of investigational medicinal product intake and collection of primary and co-primary efficacy data and with no major deviations that may affect study results.* This analysis set will be used for supportive efficacy analysis. All efficacy analysis based on the PPS will be summarized by the treatment randomized.

Each patient could either have 1 or 2 study eyes eligible for the analysis. For each patient a main (study) eye will be identified to enable a patient based presentation of analysis.

For patients with only 1 study eye (i.e. treated eye), this eye will be defined as 'Main Eye'.

For patients with 2 study eyes, the study eye with the higher corneal staining score at baseline will be considered as 'Main Eye' unless corneal staining score is not available at Week 8 Visit for this eye.

In this case, the other eye will be considered as 'Main Eye'. If both eyes are equally worse, the right eye will be the 'Main Eye'.

The eye not selected as 'Main Eye', will be called 'Secondary Eye'.

After all patients have completed study and prior to database lock, a blinded data review meeting (BDRM) will be performed to assign patients to analysis sets and to define 'Main Eyes'. Details of BDRM will be specified in a separate BDRM-plan.

The BDRM plan may consider the following criteria for exclusion of a patient from the PPS:

- *lack of compliance with investigational medical product administration*
A compliance below 80% or greater than 120% will lead to exclusion from the PPS (compliance definition please refer to section 7.2.5).
- *exposure to an IMP dose different from the one assigned to the patient*
- *missing primary or co-primary efficacy data*
- *failure to satisfy any inclusion/exclusion criteria (eligibility violations)*
- *intake of prohibited medications*

Moreover, a review of protocol deviations and potential consequences for the analysis will be evaluated during the BDRM. The results of the BDRM will be summarized in BDRM Minutes, which will be finalized before unmasking.

6.2 Subgroup Definitions

For supportive efficacy analysis, subgroup of patients with '1 study eye only' vs. '2 study eyes' will be utilized.

7 Definition of Time Points and Analysis Variables

7.1 Definition of Time Points

Analyses of endpoints will be performed based on evaluations obtained on days 0, 28±2, 56±2 and 84±2 days after discontinuation of study treatment.

Baseline will be defined as the value collected at the Baseline Visit. Study day 1 is, subsequently defined as the day after the Baseline Visit.

The Treatment Day of an event/assessment will be calculated relative to the First Study Treatment Administration as specified on the eCRF page 'Study Drug Dosing Dates',

The Treatment day of events/assessments occurring before the First Study Treatment Administration was calculated as:

- Treatment Day = (Date of assessment/event - Date of First Study Treatment Administration).

For events/assessments occurring on or after First Study Treatment Administration, Treatment Day will be calculated as:

- Treatment Day = (Date of assessment/event - Date of First Study Treatment Administration) + 1.

Visits will be analysed as they were collected. Unscheduled visits during study treatment will be considered for imputation purposes only (Last-observation carried forward).

For dropout patients, the last study visit is documented on the eCRF in the Week 8 Visit section. In this case, the visit needs to be shifted to Week 4 or Week 12 visits or Unscheduled Visit depending on the visit window specified below.

Conformance with the visit schedule will be evaluated during the BDRM. In case of substantial deviations from visit schedule, a supportive analysis will be considered to investigate influence of these deviations on primary as well as secondary endpoints and documented in BDRM minutes.

Study completers will be defined as patients, who answered the question "Did the patient complete the study" on the eCRF page 'End of Study' as YES.

Table 2: Study Visits

Scheduled Visit	Scheduled Visit Label	Scheduled Study Day	Visit Window
Baseline Visit Day 0	Baseline	0	Study day = 0
Week 4	Week 4	28	Study day in [26 – 30]
Week 8	Week 8	56	Study day in [54 – 58]
Follow-up Visit Week 12	Week 12	84	Difference Date Week 12 – Date of Last Study intake in [26 – 30]
Documented unscheduled Visits will be labeled as "Unscheduled Visit 1", "Unscheduled Visit 2".....			
For Visit Window Week 12, Date of Last Study Intake as specified on eCRF Page "Study Drug Dosing Dates"			

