If the eCRF question 'Did the event occur:' was not answered, AEs will be classified to subclass Non-TEAEs, TEAE in the Treatment Period or TEAE in the Follow-up Period based on the AE onset date utilizing the definitions given above. If this is not possible, the event will be classified as TEAE in the Treatment Period.

Missing and/or incomplete AE onset dates will be imputed for calculating relative start and stop days only. Dates will be listed as missing/incomplete [with "-" replacing missing information] but the onset Day listed between square brackets to denote it was calculated based on missing data (i.e. [1]).

Missing and/or incomplete dates will be imputed in a manner that assumes the worst case scenario:

- For a missing start day (but month and year is available), onset is assumed on the first day of the respective month.

- For a missing start month (but year is available), onset is assumed on 1st January of the respective year.
- For a completely missing start date, no imputation will be performed.

If for Non-TEAEs this procedure results in an onset date before date of informed consent, informed consent date will be used.

If for TEAEs 'During treatment period' this procedure results in an onset date before date of first study treatment, date of first study treatment will be used.

If for TEAEs 'During Follow-Up period' this procedure results in an onset date before date of Week 8 visit, date of Week 8 visit will be used.

Best Corrected Visual Acuity (BCDVA)

Best-corrected visual acuity is measured at Day 0 Baseline, Week 8 and Week 12 visit using standard charts, lighting, and procedures. All eyes must be tested at 4 meters first. When a patient cannot read at least 20 letters on the chart at 4 meters, the patient is tested at 1 meter.

In addition, the Snellen Equivalent is collected, which is based on smallest line read correctly (i.e. no or max. 1 error). The Scale is categorical and does not easily lend itself to statistical analysis or easy comparison but the logarithm of the minimal angle of resolution (logMAR) scale allows visual acuity to be assessed as a continuous measurement.

Visual acuity is recorded on the eCRF page 'Best Corrected Distance Visual Acuity'.

For the analysis, the BCDVA score and the logMAR as well as respective changes from baseline will be evaluated at Week 8 and Week 12. No imputation will be envisaged for these endpoints.

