9.6.4 Slit Lamp Examination

All grading assessments of different eye structure (excluding assessment for Other structures) will by will be summarized descriptively by treatment group and study visit for the Main Eye as well as the Secondary eye. This analysis will be performed on the SAF.

All data recorded on the eCRF page 'Slit Lamp Examination (Biomicroscopy)' will be listed.

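### Under SAP 7.1's visit relabelling, most early-termination slit-lamp and external-examination results, and nearly all early-termination BCDVA results, have no stated place in the safety summaries and would appear only in listings.

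*SAP*

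**What the plan says.** The study schedule (protocol synopsis; SAP 3.3) gives a patient who stops treatment early the Week 8 procedures, which include BCDVA, slit lamp and external ocular examination. The visit is recorded in the Week 8 section of the eCRF.

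SAP 7.1 then says that for such patients "the visit needs to be shifted to Week 4 or Week 12 visits or Unscheduled Visit depending on the visit window". SAP Table 2 sets the windows:
- Week 4: study days 26–30.
- Week 8: study days 54–58.
- Week 12: 26–30 days after the last dose.

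The same section says "Unscheduled visits during study treatment will be considered for imputation purposes only", and just before that, "Visits will be analysed as they were collected".

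For safety, SAP 7.2.8 states that "the BCDVA score and the logMAR as well as respective changes from baseline will be evaluated at Week 8 and Week 12". Slit lamp and external examination are evaluated at Baseline and Weeks 4, 8 and 12. None of these is imputed. SAP 8.3 summarises them by visit and eye. SAP 9.6.4, for example, has the slit-lamp gradings "summarized descriptively by treatment group and study visit for the Main Eye as well as the Secondary eye". SAP 9.6.3 to 9.6.5 provide listings. The table list in SAP 11 names no last-value, worst-value or early-termination table.

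**The concern.** Each rule is reasonable alone. Together they leave a gap. A termination examination that fits no window becomes Unscheduled. Unscheduled results feed imputation, and safety variables have no imputation to feed.

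The gap is widest for BCDVA. The schedule has no acuity test between baseline and Week 8, so for a patient leaving before day 54 the termination visit is often the only post-baseline acuity. Unless it meets the Week 12 window, that patient contributes no change in acuity to any summary. A patient leaving before day 26 similarly contributes no post-baseline slit-lamp result. Because SAP 8.1 reports missing values, an examined patient could be counted as missing.

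Efficacy is treated differently: SAP 7.2.7 carries forward SANDE and corneal staining and explicitly allows unscheduled visits. At stake is whether the summaries describe all examined patients or mainly those who stayed on treatment, and whether the tabulated minimum and maximum could miss an extreme value in an early leaver.

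**Working it through.** **1. Number of early leavers.** The final sample size rests on corneal staining: difference 1.0, SD 2.2, 80% power, two-sided 5%.
- Equal-arm n = 2 × (2.2 × (1.960 + 0.842) / 1.0)² ≈ 76.0, matching the plan's 76.
- n1 = 0.5 × 76 × (1 + 2) = 114 and n2 = 0.5 × 76 × (1 + 1/2) = 57.
- With 5% dropout: 114 / 0.95 = 120 and 57 / 0.95 = 60. The plan's 180 reproduces.
- Implied dropouts: 120 − 114 = 6 on rhNGF and 60 − 57 = 3 on vehicle, so 9 of 180.

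**2. Where a termination visit goes.**

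| Timing of visit | Label | Slit lamp, external exam | BCDVA |
|---|---|---|---|
| Days 1–25 or 31–53, no other window met | Unscheduled | listing only | listing only |
| Days 26–30 | Week 4 | summarised | listing only (no Week 4 evaluation) |
| Days 54–58 | Week 8 | summarised | summarised |
| 26–30 days after last dose | Week 12 | summarised | summarised |

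**3. Share affected, visit soon after last dose.** The documents do not give termination timing. Assume it is uniform over days 1–53.
- Slit lamp and external examination: 53 − 5 = 48 days unsummarised; 48 / 53 = 90.6%.
- BCDVA: 53 / 53 = 100%.

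**4. Share affected, longer lag.** Let the lag from last dose to visit run evenly over 0–30 days, but never exceed the visit day.
- Visit-day and lag pairs: days 1–30 give 2 + 3 + … + 31 = 495; days 31–53 give 23 × 31 = 713; total 1,208.
- Pairs meeting the Week 12 window: 1 + 2 + 3 + 4 + 5 = 15 on days 26–30, and 23 × 5 = 115 on days 31–53; total 130.
- BCDVA unsummarised: (1,208 − 130) / 1,208 = 89.2%.
- For slit lamp, all pairs on days 26–30 are kept (27 + 28 + 29 + 30 + 31 = 145), plus 115, giving 260. Unsummarised: (1,208 − 260) / 1,208 = 78.5%.
- With a maximum lag of 14 days the figures are 89.3% for slit lamp and 100% for BCDVA.

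**5. In patients, at 5% dropout.**
- Slit lamp and external examination: 9 × 0.785 = 7.1 to 9 × 0.906 = 8.2.
- BCDVA: 9 × 0.892 = 8.0 to 9.
- With a short lag and dropout between 2% and 15% (3.6 to 27 patients), the counts are about 3 to 24 for slit lamp and 4 to 27 for BCDVA.

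**The case against.** The strongest reply is that the SAP may not exclude these results at all. It says "Visits will be analysed as they were collected", its safety sections refer to study visits without restricting them to scheduled ones, and Table 2 defines labels for unscheduled visits. The imputation-only clause covers unscheduled visits on treatment, and a termination visit may follow the last dose. The table shells, a separate attachment, could contain a suitable row. This stands in part: the missing row is inferred from the SAP text. But the shift rule is specific to dropouts, and SAP 7.2.8 names only scheduled visits for these variables whether or not the patient is still on treatment. At the least, the two statements in SAP 7.1 conflict.

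A second reply is that the safety endpoint is TEAEs. Protocol 11.3 requires clinically relevant untoward changes in study parameters to be reported as AEs, and SAP 9.6.1 summarises events leading to withdrawal, serious events and events of special interest by arm, without visit windows. This stands, and it limits the consequence. It does not replace the summaries: AE tables count events by term and do not show the size of an acuity change, and the special-interest acuity criteria begin only above 30 ETDRS letters (or 0.6 logMAR) or at light perception.

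Third, protocol 14.4.2 asks for a final visit only where feasible, and some patients will be lost to follow-up, so nine dropouts need not mean nine examinations. This also stands; nine is a ceiling at 5% dropout.

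The blinded data review does not close the gap. Its supportive analysis of visit deviations is only to be considered, and it covers primary and secondary endpoints, not safety.

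**Conclusion.** The point holds as a gap in where early-termination safety results are summarised. As written, most slit-lamp and external-examination results from such visits before day 54, and nearly all BCDVA results, would appear only in listings. At 5% dropout that is at most about 9 of 180 patients, with 78–91% of slit-lamp and 89–100% of BCDVA termination results affected. The percentages rest on assumed uniform timing and an assumed lag from last dose.

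A reader might infer that early leavers' safety data are lost, or that patients harmed by treatment vanish from the safety tables. The documents do not support that. The values are listed, earlier scheduled visits stay in the summaries, and so do visits meeting the Week 8 or Week 12 window and slit-lamp and external examinations meeting the Week 4 window. Clinically relevant changes should reach the AE tables. Nor can it be stated as fact that the tables have no row for unscheduled visits, because the shells were not available.

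**What to change.** Keep the visit shift. Dropping it for safety would put, say, a day-10 examination in the Week 8 row and give efficacy and safety different visit definitions.

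Add one row, by arm and eye, to the BCDVA, slit-lamp and external-examination tables (SAP 9.6.3 to 9.6.5): last post-baseline value up to and including the Week 8 or early-termination visit, including unscheduled visits. This wording avoids having to decide whether a visit after the last dose counts as on treatment. Report change from baseline for BCDVA score and logMAR, and counts by category for graded, Normal/Abnormal and Yes/No items, where a change score does not suit. A worst post-baseline row is optional.

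In SAP 7.1, state how the dropout shift and the sentence on analysing visits as collected fit together.

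The cost is SAP wording, some programming on data already collected, and slightly longer tables. Trial conduct does not change. If the shells already contain such a row, a sentence in the SAP is enough.

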7.2 Analysis Variables

This chapter describes all endpoints which will be summarized as described in section 9.

7.2.1 Disposition parameters

Disposition parameters are recorded on the eCRF Page 'End of Study'.

Study discontinuations will be defined only for patients in the Enrolled Set. A patient discontinued the study prematurely, if the question 'Did the patient complete the study' was answered as 'No'.

Primary Reason for Study Discontinuation is documented on the eCRF Page 'End of Study' in categories 'Adverse Event', 'Lost to Follow-Up', 'Decision unrelated to an Adverse Event', 'Non-Compliance', 'Study terminated by the sponsor', 'Study terminated by the investigator', 'Other'.

If the study day of discontinuation as documented on the eCRF page is below 54 days, discontinuation will be considered as 'During Treatment Period', otherwise it will be considered as 'During Follow-Up Period'.

If the eCRF question 'Was the emergency envelope opened during the study?' was answered 'Yes', the patient will be considered as unmasked.

7.2.2 Demographic Characteristics

Demographic characteristics are recorded on the eCRF page "Demography".

Gender (Male, Female), Ethnicity ('Hispanic, Latino, Spanish', 'Not Hispanic, Latino, Spanish'), and Race ('White', 'Black or African American', 'Asian', 'Native Hawaiian or Other Pacific Islander', 'American Indian or Alaska Native', 'Other') will be analyzed as recorded on the eCRF.

Age (years) will be calculated at Baseline as:

- the integer part of (Date of Baseline Visit - date of birth)/365.25.
In case of incomplete dates, missing days will be set to 1st and missing months will be set to July.

7.2.3 History of Corneal Surgery and other Medical History

The details of Corneal Surgery are recorded on the eCRF page "Medical history".

The following parameters will be analysed:

- Patients with previous cataract surgery (Yes/No)
- Eyes involved in previous cataract surgery per patient (Right Eye only, Left Eye only, Both Eyes)
- Patients with previous refractive surgery (Yes/No)
- Eyes involved in previous refractive surgery per patient (Right Eye only, Left Eye only, Both Eyes)
- Patients with previous LASIK surgery (Yes/No)

- Eyes involved in previous LASIK surgery per patient (Right Eye only, Left Eye only, Both Eyes)

Identification of study eye(s) ('Right eye', 'Left eye') is recorded on the "Study Eye" eCRF page and will be analyzed as derived categories 'Both Eyes', 'Left Eye only', 'Right Eye only'.

All other medical history is recorded on the "Medical history" eCRF page.

Medical history contains information about conditions that a patient might have suffered prior to Baseline visit, or conditions that are ongoing at the time of the Baseline visit.

The medical history terms as specified by the investigator will be coded to a Preferred Term (PT) and a System Organ Class (SOC) using the Medical Dictionary for Regulatory Activities (MedDRA) thesaurus.

In the event that coding information will not be available for a specific medical history record, the record will be presented as 'Uncodable Record'. However, for final TLFs it is anticipated that all medical history records are coded.

7.2.4 Prior and Concomitant Medication

Prior and Concomitant medication data will be collected throughout the study on the 'Prior and Concomitant Medications' eCRF page. *All medications (including over-the-counter drugs, herbal products, vitamins, and antacids) taken within 4 weeks prior to the start of and throughout the study must be recorded.*

Prior medications are defined as medications that were stopped before the date of first study treatment administration, i.e. stopped on treatment day 1 or before.

Concomitant medications comprise all medications that a patient used at any stage during the treatment or Follow-up period, i.e. medications, which are ongoing at treatment day 1 or medications which started on or after treatment day 1.

Relative start and stop day of a medication will be defined as the corresponding treatment day as specified in section 7.1. If for a medication 'Ongoing' duration is specified, no stop day will be calculated.

From the above follows that a medication can either be prior or concomitant.

The Investigator Terms (Generic Medication Name, and Indication) will be coded using the Enhanced WHO-Drug Dictionary, B-Files, Version MARCH/2016.

Prior and concomitant medication data will be summarized by WHO-ATC class 2 (Therapeutic Main Class) and WHO drug name (Preferred Term).

Missing Codes or Medication Dates Imputation:

In the event that coding information will not be available for a specific concomitant medication, the concomitant medications will be presented as 'Uncodable Medication'. However, for final TLFs it is anticipated that all medication records are coded.

Missing and/or incomplete dates for prior and concomitant medications will be imputed for calculating relative start and stop days only. Dates will be listed as missing/incomplete [with "-" replacing missing information] but the Start/Stop Day listed between square brackets to denote it was calculated based on missing data (i.e. [-28], [1], [Ongoing]).

Missing and/or incomplete dates will be imputed in a manner that assumes the worst case scenario.

Technically, incomplete stop dates will be imputed as follows:

- For a missing day (but month and year is available), it will be assumed that medication have been stopped on the last day of the respective month.
- For a missing month (but year is available), it will be assumed that medication have stopped on 31st December of the respective year.
- For a completely missing stop date, the medication will be assumed as being ongoing.

Similarly, incomplete start dates will be imputed as follows:

- For a missing start day (but month and year is available), onset is assumed on the first day of the respective month.
- For a missing start month (but year is available), onset is assumed on 1st January of the respective year.
- For a completely missing start date, no imputation is performed. However, the medication will be considered as concomitant, unless indicated different by stop date.

